6.2 Dose Modification

6.2.1 Dose-cohort Study Escalation/De-escalation and Stopping Rules, Dose-Limiting Toxicities (DLTs)

Step Dose Level Determination

A decision to proceed with the next step dose of AMG 330 for each subject in cohorts 1 and 2 will be based on investigator's assessment of safety and upon approval by Sponsor.

In cohort 1, a sentinel subject will be treated first. The minimal interval between treatment start for the sentinel subject and other subjects in the cohort is 21 days. If the sentinel subject has not experienced a DLT by day 14 at █ µg/day AMG 330, he/she will proceed with 200 mg pembrolizumab on day 15 and remain at an AMG 330 dose level of █ µg/day for 7 days (until day 21). If the sentinel subject experiences a DLT during the first 7 days of treatment with AMG 330 at █ µg/day, this subject will be replaced, but the DLT will still be counted towards the study stopping rules. If the sentinel subject does not experience a DLT before or on day 21, the next subjects in the cohort may initiate dosing. If a sentinel subject experiences a DLT, the sponsor will issue a decision based on the evaluation of clinical significance of the adverse event by the DLRT and potential decisions by the sponsor may include stopping AMG 330 and/or pembrolizumab, dose de-escalation of AMG 330, or continuing therapy at full dose.

Cohort 2 will be initiated only after all subjects in cohort 1 completed study day 28 (ie, AMG 330 █ µg/day dose level in combination with pembrolizumab for 7 days), and if the rate of DLT is ≤ 3 out of 10 subjects. After receiving the DLRT recommendation, sponsor will render a final decision and will issue a written notification of the decision to investigators. Further information on dose level review meetings (DLRMs) is provided in [Section 11.3](#).

Individual Stopping Rules

Dosing for an individual will be stopped for any occurrence of a DLT. The event will be reviewed by the investigator and Sponsor for evidence of relationship to treatment and

clinical or medical significance to decide whether dosing may be resumed for the individual and any modifications to the dosing, if appropriate.

Dose Limiting Toxicities

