A DLT will be defined as any of the events described below occurring in a subject during the DLT window, unless clearly attributable to causes other than investigational product. The DLT window will start on day 1 and last for the duration of cycle 1. The CTCAE v5 will be used to assess toxicities/adverse events with the exception of CRS (see [Table 6-5](#) for grading of CRS).

DLT Evaluation

To be DLT evaluable, subjects must meet 1 of the following criteria during DLT evaluation period (cycle 1 day 1 to cycle 1 end of infusion):

- The subject experienced a DLT; OR
- The subject has received at least 70% of planned cumulative dose of AMG 330 and has not missed more than 1 dose of pembrolizumab; OR
- The subject did not experience a DLT and completed the DLT evaluation period

Events listed below are to be considered as DLTs and exceptions when occurring in a subject during the DLT window unless clearly attributable to causes other than AMG 330 and pembrolizumab treatment:

- Any treatment-related death.
- Grade 4 neutropenia lasting \geq 4 weeks from last day of cycle in absence of evidence of active AML. Note: grade 4 neutropenia maybe assessed retrospectively and outside of the DLT window
- Grade 3–4 non-hematologic toxicity not clearly resulting from the underlying leukemia EXCEPT:
 - Grade 3 fatigue, asthenia, fever, anorexia, or constipation
 - Grade 3 nausea, vomiting or diarrhea not requiring tube feeding, total parenteral nutrition, or requiring or prolonging hospitalization
 - Infection, bleeding, or other expected direct complication of cytopenias due to active underlying leukemia
 - Grade 3 infusion reaction, unless attributed to pembrolizumab, if successfully managed and which resolves within 72 hours
 - Grade 3 rash or pruritus
 - Grade 3 or 4 tumor lysis syndrome if it is successfully managed clinically and resolves within 7 days without end-organ damage.

Approved

- Grade 3 or 4 isolated analyte abnormalities (ie, those occurring without clinical consequence) that resolve, with or without intervention, to < grade 2 levels in < 72 hours will not be considered DLT.
- Grade 3 or 4 asymptomatic enzyme elevations including aspartate aminotransferase (AST), alanine aminotransferase (ALT) (without bilirubin elevation), gamma glutamyl transferase that resolve, with or without intervention, to ≤ grade 2 within 7 days will not be considered a DLT, unless attributed to pembrolizumab.

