- Isolated grade 3 elevation of amylase or lipase not associated with clinical or radiological evidence of pancreatitis
- Grade 3 endocrinopathy that is well controlled by hormone replacement
- CRS meeting any of the criteria listed below:
 - Grade 2 CRS that does not resolve, with or without intervention to grade 1 within 7 days will be considered a DLT
 - Grade 3 CRS that does not resolve, with or without intervention to ≤ grade 2 within 5 days, will be considered a DLT
 - Any grade 4 CRS
- Any grade 5 toxicity
- Receive less than 70% of the planned cumulative dose of AMG 330 or miss more than 1 dose of pembrolizumab during the first cycle due to investigational product(s) related toxicity that does not meet the DLT criteria listed above

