6.2.2 Dosage Adjustments, Delays, Rules for Withholding or Restarting, Permanent Discontinuation

6.2.2.1 Amgen Investigational Product: AMG 330

Subjects will be monitored continuously for adverse events while on study therapy.

Subjects will be instructed to notify their physician immediately for any and all adverse events. The criteria presented in this section for dose modifications and delays for AMG 330 are meant as general guidelines.

Criteria for Dose Delay or Dose Reduction

Subjects will receive continuous AMG 330 therapy as long as they have not had disease progression or an adverse event requiring dose modification, as described below.

Subjects who experience a grade 4 non-hematologic adverse event will not receive additional protocol-related therapy and will be removed from study unless discussed and agreed upon by the Sponsor and investigators that it is in the best interest of the subject to receive additional therapy with AMG 330 (eg, if the subject has demonstrated a response to therapy).

Dose modifications, interruptions, or delays may occur in the setting of lower grade adverse events based on the clinical judgement of the investigator, and in consultation

with the sponsor. Dose reductions should be to the previous lower dose level, or to a dose level in between the previous dose level and the current dose level, after discussion between the investigator and the sponsor.

No more than 2 dose level reductions of AMG 330 will be allowed per subject. If a third dose reduction is required, the subject must discontinue AMG 330 (and pembrolizumab, if receiving combination therapy based on response to therapy). Dose re-escalation after a dose reduction may occur in limited circumstances (such as a change in attribution of adverse event, or if re-escalation is in the best interest of the subject) after discussion and agreement between the sponsor and the investigator.

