For an adverse event requiring dose modification, AMG 330 (and pembrolizumab for subjects receiving combination therapy) should be interrupted to allow recovery from the adverse event. Re-initiation of study drug cannot occur until adverse event decreases to grade ≤ 1 . In case of delayed recovery to grade ≤ 1 from treatment-related adverse events that results in a delay of treatment for > 21 days, the subject will not receive additional protocol-related therapy and will be removed from study unless discussed and agreed upon by the sponsor and investigators that it is in the best interest of the subject to receive additional therapy with AMG 330 and pembrolizumab (eg, if subject demonstrated response to therapy).

Assessment of causality (chronology, confounding factors such as disease, concomitant medications, diagnostic tests and previous experience with the agent) must be determined and documented by the investigator, prior to dose modification.

In case of grade 2 CRS, administration of AMG 330 can be continued on the currently tested dose level for 8 hours, and treatment provided to mitigate CRS symptoms. If symptoms do not improve to grade 1, the dose will be de-escalated by 50% for an additional 24 hours. If CRS grade 2 resolves to grade 1, the dose can be re-escalated back to the level being tested. If symptoms persist, AMG 330 infusion will be interrupted and pembrolizumab infusion will be delayed until symptoms improve to grade 1. If treatment is interrupted for < 24 hours, the interrupted AMG 330 dose can be resumed and re-escalated back to the tested dose level. If treatment is interrupted for > 24 hours, restart or repeat rules apply (see below).

In case of grade 3 CRS, AMG 330 treatment must be interrupted and pembrolizumab treatment postponed. Sponsor has to be consulted prior to a planned re-start. In case

of grade 4 CRS, treatment must be permanently discontinued. See [Section 6.8](#) for specific instructions for the management of CRS.

If the same grade 3 non-hematologic adverse event recurs despite a dose reduction, a second dose reduction versus discontinuation of the subject from further protocol therapy should be discussed and agreed upon the sponsor and investigators.

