If a DLT occurs in a subject with clinical benefit from treatment, a restart at a lower dose can be considered if the toxicity has resolved to grade ≤ 1 and after consultation with the sponsor. If AMG 330 is discontinued, pembrolizumab may be continued as a monotherapy until disease progression for a maximum of 35 cycles (approximately 2 years) after discussion and agreement between the sponsor and the investigator. If pembrolizumab is discontinued, AMG 330 may be continued as a monotherapy.

Dose delay: treatment should be interrupted until the adverse event is resolved to grade ≤ 1 , and can then be resumed at the same dose unless the interruption lasted for more than 24 hours, please see below. (Note: if the event needs > 21 days to resolve, treatment has to be permanently discontinued, see also below).

Infusion Interruption

Significant events requiring a change in treatment will be managed by immediate infusion interruption:

- The subject experiences a DLT as defined in [Section 6.2.1](#)
- The subject experiences a clinically relevant grade 4 adverse event related to investigational product (see above) but does not meet the DLT criteria
- The subject meets criteria for discontinuation of investigational product as described in [Section 6.2.2](#)
- The subject experiences disease related adverse events and AMG 330 interruption is required for medical interventions
- Technical problem with the infusion pump
- The investigational product is incorrectly prepared or administered (eg, overdose)

Restarting the Infusion

Treatment may resume if the interruption is ≤ 21 days and if:

- The interruption occurred due to other reasons than toxicity (disease-related events, technical or logistic reasons; eg, diagnostic measurements). The infusion can be restarted at the same dose and without additional measures.
- The toxicity has resolved to CTCAE v5 grade ≤ 1 (in case of dose reduction, infusion may be re-started without prior resolution of the toxicity to CTCAE v5 grade ≤ 1 if the adverse event is not clinically relevant and upon discussion and agreement between the investigator and the sponsor)

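### Grade 4 CRS and treatment-related toxicity delays beyond 21 days are permanent stops in some clauses of Protocol 6.2.2 and 6.8, while other clauses leave restart or continued pembrolizumab open

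*Protocol*

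**What the plan says.** **Grade 4 CRS: the stops.** Protocol 6.2.2.1 (Criteria for Dose Delay or Dose Reduction) states that in case "of grade 4 CRS, treatment must be permanently discontinued" and sends the reader to Section 6.8. The grade 4 row of Table 6-5 there permanently ends both drugs. The restart text after that table opens a route only after grade 3 CRS.

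**Grade 4 CRS: the permissions.** Section 6.2.1 counts "Any grade 4 CRS" as a DLT, and "The DLT window will start on day 1 and last for the duration of cycle 1". Section 6.2.2.1 then says: "If a DLT occurs in a subject with clinical benefit from treatment, a restart at a lower dose can be considered", subject to recovery to grade 1 or less and consultation with the sponsor. The first bullet under Permanent Discontinuation in the same section carries a similar exception, followed directly by a list whose first item is grade 4 CRS. On the second drug, Section 6.2.2.1 says: "If AMG 330 is discontinued, pembrolizumab may be continued as a monotherapy until disease progression for a maximum of 35 cycles", after sponsor and investigator agree. Section 6.2.2.2.1 gives a similar permission on the same condition.

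**The 21-day rule.** Section 6.2.2.1 bars further therapy when slow recovery from a treatment-related event delays treatment more than 21 days, unless sponsor and investigators agree that continuing is in the subject's best interest. The note under Dose delay, later in that section, requires permanent discontinuation if the event takes more than 21 days to resolve. The Permanent Discontinuation list includes an interruption of more than 21 days for an adverse event not clearly due to the leukemia. Neither later clause mentions the waiver.

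**The concern.** A site with a subject in either situation can find one clause that forbids re-exposure and another that allows it. Grade 4 CRS is life-threatening by the definition in Table 6-5. CRS was the most frequent adverse event in the monotherapy study (31 of 49 subjects, 63.3%, Section 4.3). Section 2.3 warns that blocking PD-1 may lead to higher grades of CRS, and Section 2.2.2.3 records that no combination toxicology studies were done.

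The permissive clauses are aimed at subjects who are benefiting, which is when the pressure to resume would be greatest. With about 5 sites planned (Section 4.2.2), sites could also read the same text differently. What is at stake is subject safety and consistent conduct, not a statistical quantity.

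**Working it through.** The plan gives no figure to reproduce and no arithmetic applies. The check is to take one subject in each situation through every relevant clause.

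**Subject A: grade 4 CRS in cycle 1, clear clinical benefit, event settled to grade 1 or less, sponsor consulted.**

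| Protocol clause | AMG 330 | Pembrolizumab |
|---|---|---|
| 6.2.2.1, CRS paragraph | Permanent stop | Covered by the general word treatment |
| Table 6-5, grade 4 row | Permanent stop | Permanent stop |
| 6.8, restart after CRS | Route given after grade 3 only | Not addressed |
| 6.2.2.1, DLT restart paragraph | Lower-dose restart may be considered | May continue by agreement if AMG 330 is discontinued |
| 6.2.2.1, Permanent Discontinuation, first bullet | Listed as a stop, with a restart exception in the same bullet | Not addressed separately |
| 6.2.2.2.1 | Not addressed | May continue by agreement if AMG 330 is discontinued |

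1. Section 6.2.1 makes the event a DLT without further condition, so both DLT exceptions apply on their face.
2. The words *This includes* in the Permanent Discontinuation bullet can attach to the stop or to the exception. If they attach to the stop, grade 4 CRS is one of the listed toxicities, and the exception, written for a DLT in general, still covers it. If they attach to the exception, grade 4 CRS is named as an event after which restart may be considered. Neither reading takes grade 4 CRS out of the exception.
3. For pembrolizumab, stopping AMG 330 for grade 4 CRS meets the opening condition of both continuation clauses, while Table 6-5 stops pembrolizumab too.
4. Reach: the AMG 330 conflict depends on DLT status and so concerns cycle 1. The pembrolizumab conflict does not depend on the cycle.

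**Subject B: treatment-related toxicity that takes more than 21 days to reach grade 1 or less.**

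| Clause in 6.2.2.1 | Outcome |
|---|---|
| Criteria for Dose Delay or Dose Reduction | No further therapy unless sponsor and investigators agree otherwise |
| Dose delay note | Permanent discontinuation, no exception |
| Permanent Discontinuation list | Permanent discontinuation, no exception |

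The scopes differ slightly: the waiver covers treatment-related events, and the list covers events not clearly due to the underlying disease. A treatment-related event ordinarily falls under both. The note's only cross-reference points forward, away from the waiver.

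**The case against.** The strongest reply is that a specific mandatory rule limits a general permissive one. The CRS paragraph points to Section 6.8, and the text on restarting the infusion also sends CRS cases there. Section 6.8 stops both drugs at grade 4 and offers restart only after grade 3. This is good evidence that the absolute stop is intended. It does not settle the matter, because the protocol states no order of precedence and the Permanent Discontinuation bullet puts grade 4 CRS and the exception side by side. It also does nothing for the 21-day rules, where neither side is the more specific.

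A second reply is that "The criteria presented in this section for dose modifications and delays for AMG 330 are meant as general guidelines". That sentence does not rank the rules against each other and does not extend to Table 6-5. A third is that every clause relied on here requires sponsor consultation or agreement. This is a real safeguard and limits the risk, but it leaves the contradiction in the text.

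A reader might infer a wider problem. The documents do not support these stronger readings:

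- **Individual Stopping Rules (6.2.1).** The review of "clinical or medical significance to decide whether dosing may be resumed for the individual and any modifications to the dosing, if appropriate" grants no permission. A review that applies Table 6-5 and refuses resumption satisfies both texts.
- **Grade 4 waiver in 6.2.2.1.** The rule beginning "Subjects who experience a grade 4 non-hematologic adverse event will not receive additional protocol-related therapy and will be removed from study unless discussed" could be read to reach CRS, but the DLT list treats CRS apart from non-hematologic toxicity and grades it on its own scale, so this is arguable at best.
- **Pembrolizumab statements in 4.1 and 4.4.2.** These are design and duration summaries. They list no toxicity stops at all, so their silence on grade 4 CRS shows nothing.
- **Recovery wording.** The Permanent Discontinuation exception asks only that the toxicity has resolved, but the general rule in 6.2.2.1 already bars re-initiation above grade 1.
- **Restarting the Infusion.** The clause allowing resumption within 21 days is permissive. It does not say that resumption is possible only then, so it is not a third prohibition.

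**Conclusion.** Two contradictions stand. For grade 4 CRS, the permanent stop in Section 6.2.2.1 and Table 6-5 conflicts with two DLT restart clauses in 6.2.2.1 and with the pembrolizumab continuation clauses in 6.2.2.1 and 6.2.2.2.1. For treatment-related delays beyond 21 days, one clause of 6.2.2.1 can be waived by agreement and two cannot.

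The size is modest. The conflicting clauses permit and do not require, so a sponsor that always stops complies with every one of them. It would be wrong to conclude that the protocol directs re-exposure after grade 4 CRS. The documents give no grade 4 CRS rate, so any probability of the clause being used would rest on an invented input, and none is offered. Analysis sets, DLT counts and sample size are unaffected: a subject with a DLT is DLT-evaluable under Section 6.2.1 whether or not dosing resumes. The conclusion rests on the text alone. The correction should be made, because it removes a written permission for re-exposure after a life-threatening event at almost no cost.

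**What to change.** **Grade 4 CRS.**
- In the DLT restart paragraph and the first Permanent Discontinuation bullet of Section 6.2.2.1, state that the restart exception does not apply to grade 4 CRS.
- In that bullet, put the list of toxicities before the exception, so that the list plainly describes the stops.
- In Sections 6.2.2.1 and 6.2.2.2.1, state that pembrolizumab may not continue after grade 4 CRS, as Table 6-5 requires.

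**21 days.** Use one rule in all three places in Section 6.2.2.1. Either delete the waiver, or keep it and cite it in the Dose delay note and the Permanent Discontinuation list as the only exception. Which to choose is the sponsor's clinical decision.

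**Cost.** A few sentences of protocol wording in Sections 6.2.2.1 and 6.2.2.2.1. Sections 6.2.1, 4.1 and 4.4.2 and the grade 4 non-hematologic waiver need no edit for this point, and there is no change to the analysis or sample size.

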6.1.1.2 AMG 330 Inpatient Dosing

Subjects are required to be monitored in a hospital for a minimum of 72 hours following initiation of therapy and for a minimum of 72 hours after each dose level increase. Close monitoring is indicated because of the potential adverse events associated with T cell redistribution and potential cytokine release effects triggered by the administration of

AMG 330. Nurses/physicians familiar with such conditions should be available for immediate intervention in case of complications.

Also, if AMG 330 is interrupted for longer than 4 hours, re-start of the infusion should be performed in the hospital, under the supervision of the investigator or designee. The subject should be observed overnight for possible side effects after the re-start, either in the hospital or in the outpatient setting as applicable. Administration of dexamethasone premedication will occur as described in [Section 6.7](#).

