Please also refer to specific guidance on restart after CRS in [Section 6.8](#). Restarting the infusion after a treatment interruption requires care. The re-start should be performed in the hospital, under supervision of the investigator or designee, if the reason for the interruption was other than a technical issue or the interruption exceeded 4 hours independent of reason. Assessments should be performed after infusion re-start depending on the length of the interruption. The subject should be hospitalized for at least 48 hours after re-start of the infusion.

In case of an AMG 330 infusion interruption of > 24 hours, regardless of the reason for interruption, re-start of the infusion (repeat cycle) should be performed using step doses, which will be defined upon consultation with the sponsor. Only 2 repeat cycles may be performed in cycle 1. For cycle 2 and beyond, additional repeat cycles can be permitted upon discussion and agreement between the investigator and sponsor.

Step doses will be performed within 1 – 2 weeks (\pm 1 day) to return to the interrupted AMG 330 dose level, and the number and duration of repeat step doses will depend on the level of interrupted AMG 330 dose. During this 1-2 weeks, [Table 1-7 Schedule of Activities](#) should be followed (eg, for AMG 330 doses interrupted at [REDACTED] μ g/day and below, 2 step doses can be used: [REDACTED] μ g/day for 3 days followed by [REDACTED] μ g/day for 4 days; for doses interrupted above [REDACTED] μ g/day, 3 step doses can be used: [REDACTED] μ g/day for 1 day followed by [REDACTED] μ g/day for 3 days followed by [REDACTED] μ g/day for 3 days). In case of AMG 330 infusion interruption for < 24 hours, regardless of the reason for interruption, restart of infusion should be performed at the same dose level as the last dose level. Administration of pembrolizumab will remain on the Q3W schedule.

After 2 unsuccessful restarts, the subject may remain on the study and continue AMG 330 treatment with a previously tested target dose that has been well tolerated. The dose of pembrolizumab will remain unchanged.

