Re-start of Treatment after Infusion Interruption due to Cytokine Release Syndrome:

After interruption of AMG 330 infusion due to grade 3 CRS, the infusion may be re-started if all of the following criteria are met:

- Sponsor must be consulted prior to re-starting treatment
- The event has resolved to grade ≤ 1 prior to re-starting treatment

In case of an infusion interruption of > 24 hours, regardless of the reason for interruption, re-start of the infusion should be performed at the initial dose and dose steps should be performed prior to administering the interrupted dose. The dose level for each step and number of steps should be determined in consultation with the Sponsor prior to re-initiation of the infusion.

Tumor Lysis Syndrome

Subjects with AML and WBC < 10 000/ μ L are considered to be at low risk for tumor lysis syndrome. WBC > 10 000/ μ L and < 50 000/ μ L are considered to be at intermediate risk, and subjects with WBC > 50 000/ μ L are considered at high risk. This protocol requires that subjects have a maximum WBC count of 15 000/ μ L.

Additional high risk features include baseline uric acid > 450 μ g/L (7.5 mg/dL), serum creatinine > 1.4 mg/dL, and lactate dehydrogenase (LDH) greater than the upper limit of normal (ULN).

Patients with intermediate risk WBC count and elevated baseline uric acid (> 450 μ g/L), serum creatinine > 1.4 mg/dL, or LDH greater than ULN will be recommended to receive allopurinol prophylaxis. Typical dosing is 600-800 mg/day administered bid or qid and should begin 3 days before the first dose of study drug. Patients should be well hydrated and supplemented with IV fluid as clinically indicated.

For grade 3 and 4 tumor lysis syndrome, please see [Section 6.2.1](#) for DLT considerations.

Infection Prophylaxis

Subjects who may experience neutropenia for 7 days or longer are at a high risk for infectious complications. As appropriate, these subjects should be administered prophylactic antibacterial (eg, fluoroquinolones), antifungal and antiviral medications. These subjects should be monitored for early signs of breakthrough infections after the initiation of antibacterial therapy to prompt additional evaluation and possible therapy modification.

7. Discontinuation Criteria

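### Protocol 6.2.2.1: read literally, the first restart bullet lets AMG 330 resume at full dose with no precautions after any non-toxicity stop of up to 21 days, contradicting the 24-hour and hospital-restart rules that follow it

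*Protocol*

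**What the plan says.** Under Restarting the Infusion, Protocol Section 6.2.2.1 lists when treatment may resume after a stop of 21 days or less. The first bullet covers any reason other than toxicity, naming disease-related, technical and logistic reasons. It then says: "The infusion can be restarted at the same dose and without additional measures". It sets no shorter time limit and refers to no other rule.

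Other text covers the same restarts:

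- **Step doses after more than 24 hours.** Section 6.2.2.1 says that, "regardless of the reason for interruption, re-start of the infusion (repeat cycle) should be performed using step doses". Section 6.8 repeats this: "regardless of the reason for interruption, re-start of the infusion should be performed at the initial dose and dose steps should be performed".
- **Repeat cycle.** Section 6.2.2.1 calls for a new repeat cycle when the cycle was interrupted for more than 24 hours but less than 21 days.
- **Dexamethasone.** Sections 6.1.4 and 6.7.2 require 8 mg IV before a restart after more than 24 hours. Section 6.2.2.1 requires it before the restart and before each step.
- **Hospital restart.** Section 6.2.2.1 requires it "if the reason for the interruption was other than a technical issue or the interruption exceeded 4 hours independent of reason". Section 6.1.1.2 agrees above 4 hours: "if AMG 330 is interrupted for longer than 4 hours, re-start of the infusion should be performed in the hospital". Section 6.1.1.3 requires a supervised restart in clinic or hospital above 4 hours.
- **Observation afterwards.** Section 6.2.2.1: "The subject should be hospitalized for at least 48 hours after re-start of the infusion". Section 6.1.1.3 also sets a 48-hour minimum. Section 6.1.1.2 instead says: "The subject should be observed overnight for possible side effects after the re-start, either in the hospital or in the outpatient setting as applicable". When step doses are used, Section 6.2.2.1 keeps the subject in hospital until 72 hours after the dose step.

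**The concern.** For one and the same event, a non-toxicity stop of more than 24 hours, the bullet says same dose and nothing more, while the later text says step doses, dexamethasone and hospital. A site cannot follow both.

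The omitted measures are the protocol's safeguards against cytokine release syndrome (CRS). Section 6.1.4 gives CRS prevention as the purpose of dexamethasone. Section 6.1.1.2 explains inpatient monitoring this way: "Close monitoring is indicated because of the potential adverse events associated with T cell redistribution and potential cytokine release effects". Section 2.2.2 reports that dose steps were introduced after grade 3 CRS and reduced its frequency and severity. Section 2.3 warns that PD-1 blockade may lead to higher grades.

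There is also a link to the primary endpoint. Under Section 6.2.2.1, a cycle interrupted for more than 24 hours is followed by a repeat cycle and is not evaluable for dose-limiting toxicity (DLT), unless the event behind the stop was itself a DLT. A site that followed the bullet would carry on with the interrupted cycle, and its DLT status would be unclear.

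**Working it through.** The plan states no figure to reproduce. The check compares the rules by reason and length of interruption.

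**Limits used.** Bullet: up to 21 days (6.2.2.1). Step doses and dexamethasone: more than 24 hours (6.1.4, 6.2.2.1, 6.7.2, 6.8). Repeat cycle: more than 24 hours and less than 21 days (6.2.2.1). Same dose level: less than 24 hours (6.2.2.1). Hospital restart: more than 4 hours for any reason, or any length if not technical (6.2.2.1).

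| Non-toxicity interruption | What the other rules require | Conflict with the bullet |
|---|---|---|
| Technical, up to 4 h | Same dose; no hospital restart triggered | None, if the 48-hour sentence is read with the paragraph it closes |
| Technical, over 4 h and under 24 h | Same dose; hospital restart; at least 48 h in hospital | Measures only |
| Logistic, diagnostic or disease-related, under 24 h | Same dose; hospital restart at any length; at least 48 h in hospital | Measures only |
| Any reason, over 24 h to 21 days | Step doses; new repeat cycle (to under 21 days); dexamethasone; hospital restart; stay until 72 h after the dose step | Dose and measures |

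Exactly 24 hours falls under neither dose sentence in Section 6.2.2.1.

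**Extent of the dose conflict.** The bullet covers 21 × 24 = 504 hours. The part above 24 hours is 504 − 24 = 480 hours, and 480 / 504 = 95%. This is a share of the permitted duration range. It is not a share of the interruptions to be expected, most of which may be short.

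**Neighbouring text.** The dose-delay line just before the restart rules allows the same dose, excepts interruptions of more than 24 hours and points to the text below. It concerns adverse events only. The non-toxicity bullet has no such exception.

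**Observation after a restart.** For an interruption of more than 4 hours, Section 6.1.1.2 accepts overnight observation, possibly as an outpatient, whereas Sections 6.1.1.3 and 6.2.2.1 require at least 48 hours in hospital. This disagreement is separate from the bullet.

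**The case against.** The strongest reply is that the protocol already shows which rule governs. The bullet turns on the reason for the stop, and the paragraphs that follow expressly set reason aside. The repeat-cycle sentence covers almost exactly the disputed window. The bullet can also be read as saying when treatment may resume, with the later text saying how. Other controls treat a stop of more than 24 hours as a distinct event: step doses are defined with the sponsor, only two repeat cycles are allowed in cycle 1, and three such interruptions in cycle 1 end treatment. Section 6.1.1.1 asks that technical and logistic stops be as short as possible. Section 6.2.2.1 calls its dose-modification and delay criteria general guidelines.

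Most of this stands. A reader might infer that the protocol leaves the choice between the two instructions open. The documents do not support that, because the stricter rules are evidently intended. What survives is that the bullet also speaks to the manner of restart, by naming the dose and waiving other measures. Section 6.1.1.1's request for short stops does not cover disease-related interruptions, which the bullet does. Calling criteria guidelines does not reconcile two opposite instructions.

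A reader might also infer that the 48-hour sentence forces a hospital stay after a brief pause for a pharmacokinetic sample through the central line (Section 8.2.7). That reading is strained. The sentence closes the paragraph on hospital restarts, and Section 6.1.1.3 ties the 48 hours to interruptions of more than 4 hours.

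**Conclusion.** The contradiction is real and lies in the wording. On dose, step doses, repeat cycle and dexamethasone it is confined to non-toxicity stops of more than 24 hours. On the setting of the restart it begins earlier: above 4 hours for technical stops, and at any length for other reasons. Below 24 hours the bullet and the later text agree on dose.

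The edit is worth making because the instruction at fault, followed as written, removes CRS safeguards, and the correction costs almost nothing. The conclusion assumes only that a site may act on the bullet without reading on.

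A reader might infer that subjects will be restarted unsafely. The documents do not support that: they give no interruption rate, no CRS rate after a restart without steps, and no indication of how sites would read the bullet. The 63.3% CRS incidence in Section 4.3 is an overall monotherapy figure and does not measure this risk.

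**What to change.** In Section 6.2.2.1, replace the second sentence of the first restart bullet with:

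> If the interruption lasted ≤ 24 hours, the infusion can be restarted at the same dose, subject to the hospital-restart rule below; if it lasted > 24 hours, the step-dose/repeat-cycle, dexamethasone and hospitalization rules below apply regardless of the reason.

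This also settles the case of exactly 24 hours for non-toxicity stops. Changing the same-dose sentence later in that section from less than 24 hours to 24 hours or less would match it.

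Separately, replace the overnight-observation sentence in Section 6.1.1.2 with a cross-reference to the stay of at least 48 hours in Sections 6.1.1.3 and 6.2.2.1. State in Section 6.2.2.1 that the 48-hour sentence applies to restarts that must be done in hospital. The stay until 72 hours after the dose step continues to apply when step doses are used.

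The exemption for technical issues should not be widened to logistic or diagnostic stops as part of this edit. Section 6.2.2.1 now requires a supervised hospital restart for those at any length. Relaxing that is a clinical decision for the sponsor.

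The cost is a few sentences in an amendment and no procedure that the protocol does not already require. Compared with Section 6.1.1.2 read alone, a restart after more than 4 hours moves from overnight observation to the 48-hour stay already required elsewhere.
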